The SEARCH SAPPHIRE Hypertension Linkage study is an individual randomized controlled trial, designed to test the hypothesis that a transportation voucher and a follow-up phone call will improve linkage to clinic-based hypertension care following community-based screening. The trial takes place in three communities in Kenya and Uganda and began enrollment in June 2021. After community-based screening, individuals diagnosed with hypertension (HTN) were enrolled and given a clinic appointment at the nearest government-run clinic. Participants randomized to intervention (n=100) received a voucher to reimburse transport expenses, redeemable upon clinic linkage at any time following enrollment (even if initial linkage appointment was missed). Intervention participants who missed their initial linkage appointment also received a follow-up phone call to encourage linkage. Control participants (n=100) did not receive a transport voucher or any follow-up if they missed their initial linkage appointment. Upon linkage to care, all participants received integrated, patient-centered hypertension care, detailed elsewhere.¹⁻³ Treatment guidelines for use of antihypertensive medication were based on standard country guidelines. Additional details of the study procedures are available in the Study Protocol.

The primary objective of this study is to determine whether the intervention improved linkage to HTN care by 30 days. Secondary endpoints include linkage at or before the scheduled appointment, linkage by 3 months, HTN control at follow-up, and retention in hypertension care. We will also characterize changes in HTN severity and evaluate predictors of linkage, HTN control, and retention.

Throughout, the population of interest comprises non-pregnant adults, aged 25 years and older, who do not have a prior diagnosis of hypertension, and who have uncontrolled HTN at baseline as identified through community-based screening (defined as systolic blood pressure ≥ 140 mmHg or diastolic blood pressure ≥ 90 mmHg on all three baseline measures). Participants were excluded if they had a blood pressure $\geq 180/110$ mmHg and had symptoms of hypertensive emergency – these individuals were immediately transported to the nearest health facility for emergent treatment.

We will provide descriptions of participant flow through the study (i.e., a consort diagram), measurement coverage, and baseline characteristics (e.g., country, age, sex, marital status, occupation, monthly income, education, comorbidities, and baseline severity of hypertension), overall and by arm and sex. We will also report risk factors (N and %) for uncontrolled HTN at baseline, overall and by sex. Additionally, we will report and describe intervention fidelity and delivery of clinical hypertension care. Finally, we will report and describe barriers and facilitators of hypertension care engagement, as assessed through participant self-report at baseline and follow-up.

2.1 General approach for evaluating intervention effects

We will assess the intervention effect with targeted minimum loss-based estimation (TMLE), which provides precision and power gains over an unadjusted analysis by adjusting for baseline predictors of the outcome.⁴⁻⁷ For a detailed review of TMLE and its relation to other effect estimators in randomized trials, we refer the reader to Colantuoni and Rosenblum.⁸ For a recent demonstration of the improved precision offered by TMLE in randomized trials, we refer the reader to Balzer et al. and to Benkser et al..^{9,10}

Here, we will use **TMLE with Adaptive Pre-specification**, a fully automated procedure to flexibly adjust for baseline outcome predictors, while maintaining Type-I error control.¹¹ Specifically, using 10-fold cross-validation, we will chose the optimal approach for estimating the expected outcome given the randomization arm and baseline covariates (a.k.a., the outcome regression) and for estimating the conditional probability of being randomized to the intervention given the baseline covariates (a.k.a., propensity score). Throughout, optimality is defined by using the squared influence curve for the TMLE as loss function. Thereby, we will select the combination of estimators (adjustment variables + approach) of the outcome regression and of the propensity score that minimizes the cross-validated risk estimate and, thus, the cross-validated variance estimate.

Our pre-specified, candidate adjustment variables are age, sex, hypertension severity (“grade 1” as 140-159/90-99 mmHg versus “grade 2 or higher” as $\geq 160/100$ mmHg), site, and nothing (i.e., unadjusted). Our pre-specified, candidate estimators of the outcome regression are main terms, stepwise regression, stepwise regression with all possible pairwise interactions, LASSO, and the mean. Our pre-specified, candidate estimators of the propensity score are main terms, stepwise regression, LASSO, and the mean. In sensitivity analyses, we will also implement that unadjusted effect estimator as the contrasts of average outcomes by arm.

For all endpoints, primary estimates will be for the study sample and on the **relative scale**: $1/n \sum_{i=1}^n Y_i(1) \div 1/n \sum_{i=1}^n Y_i(0)$, where $Y_i(1)$ denotes the counterfactual outcome for participant i under the intervention and $Y_i(0)$ denotes the counterfactual outcome for participant i under the control. Secondary comparisons will be on the absolute scale.

For all endpoints, we will test the **null hypothesis** of no improvements in outcomes due to the intervention with a one-sided test at the 5% significance level. We will also report point estimates and 95% confidence intervals for each effect measure and the arm-specific average outcomes. Standard error estimation will be with the estimated influence curve, and statistical inference will follow from the Central Limit Theorem (i.e., using the standard normal distribution).⁴

For all endpoints, we will also examine the intervention effect within **subgroups** defined by sex, age group (<60 years vs. ≥ 60 years), country, site, baseline HTN severity, and HIV status. In subgroups with fewer than 41 participants, we will limit the candidate estimation approaches to main terms adjustment for a single covariate or the simple mean.

2.2 Evaluate the effect on linkage to hypertension care at 30 days

The primary endpoint is linkage to care by 30 days, evaluated with clinical records. Participants without clinical records indicating linkage to care will be assumed never to have linked. Sensitivity analyses will incorporate self-report, defined as having a clinical record of linkage by 90 days or self-reported linkage to any health facility within the past 3 months. These linkage endpoints are not subject to missingness.

As described above, we will use TMLE with Adaptive Pre-specification to compare linkage to care by 30 days between intervention and control arms and to test the null hypothesis that the intervention did not improve linkage to care by 30 days. Sensitivity analyses incorporating self-report and subgroup analyses will be implemented analogously.

We will also provide descriptive statistics of participants who linked to care by 30 days. Finally, we will generate a graphic of cumulative linkage over time by arm.

2.3 Evaluate the effect on linkage to scheduled post-screening appointment

To assess the effect of the transport voucher, we will again use TMLE to compare linkage to care by the scheduled appointment date between intervention and control arms. We will use the same candidate adjustment variables and approaches as the primary endpoint. This endpoint is also not subject to missingness. We will formally test the null hypothesis that the intervention did not improve linkage to care on or before the scheduled linkage appointment. We will also implement analogous subgroup analyses and provide descriptive statistics of participants who linked to care by their scheduled appointment date.

To elucidate the added value of the transport voucher, we will also compare the intervention effect on linking by 30 days (overall) to the intervention effect on linkage to the scheduled appointment. To do so, we will use the Delta Method to test the null hypothesis that the ratio of relative risks is 1 and that the difference of absolute effects is 0. Here, we will use a two-sided test at the 5% significance level.

2.4 Evaluate the effect on hypertension control at months 3, 6, and 12

Again using TMLE with Adaptive Pre-specification, we will assess the intervention effect on HTN control (all three blood pressure measures $<140/90$ mmHg) at months 3, 6 and 12 post-enrollment. We will formally test the null hypothesis that the intervention did not improve hypertension control at these timepoints. We will use the same candidate adjustment variables and approaches as the primary endpoint (linkage within 30 days).

In the primary analysis of hypertension control, participants who do not have their blood pressure measured within the endpoint date (e.g., in the window of 2.5-3.5 months post-enrollment for the 3-month endpoint) will be considered to have uncontrolled hypertension. In sensitivity analyses, we will control for incomplete ascertainment of blood pressure measures. These secondary analyses will use TMLE to estimate the intervention effect, while adjusting for differences in characteristics (e.g., arm, sex, age, severity, site) between persons with measurements and persons with missing measurement.

We will again implement subgroup analyses as well as examine control among participants who linked to HTN care within 30 days. We will also evaluate the

intervention impact on HTN severity, defined as participants with grade 2 or higher HTN at follow-up, and on the average of the second and third systolic blood pressure measures at follow-up.

2.5 Evaluate the effect on retention in hypertension care at 3, 6 and 12 months

We will define retention in care as not late for the most recent scheduled hypertension care appointment by 30 days or more. This endpoint is also not subject to missingness. Again, we will use the primary analytic approach of TMLE with Adaptive Pre-specification to assess the intervention effect on retention in hypertension care at 3, 6 and 12 months and to test the null hypothesis that the intervention did not improve retention in care at 3, 6 or 12 months, respectively. For this endpoint, the candidate adjustment variables will be expanded to include baseline HIV status. We will implement analogous subgroup analyses.

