4.2. Study Hypothesis for Primary Objective

Each of the Phase A studies will test a hypothesis related to the intervention:

- Dynamic Choice Prevention delivered to women seen at antenatal clinics (ANC) will improve biomedical covered time, defined as the proportion of follow-up time that a participant is protected from HIV with either PrEP or PEP.
- Dynamic Choice Prevention delivered to men and women seen at the outpatient department (OPD) will improve biomedical covered time, defined as above.
- Dynamic Choice Prevention delivered to men and women seen in the community by village health teams (VHTs) will improve biomedical covered time, defined as above.
- Dynamic Choice Treatment delivered to mobile persons with HIV will improve HIV viral suppression at 48 weeks.
- The Healthy Living Intervention delivered to persons with HIV and heavy alcohol use will improve HIV viral suppression at 24 weeks.
- A one-time transport voucher will increase linkage to hypertension care following community-based diagnosis.
- Community-based hypertension care will improve hypertension control among persons with severe hypertension.

The study hypothesis for the Phase B population level study is: A Precision Community Health Model leveraging existing facility-based outreach and community health workers, enabled by dynamic choice prevention/treatment multi-disease approaches and interactive data systems –will reduce HIV infections, deaths and improve health.

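### In the hypertension linkage SAP, comparing the 30-day effect with the appointment-date effect cannot isolate the transport voucher or the phone call

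*SAP*

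**What the plan says.** The SAP's opening description of the hypertension linkage trial gives the hypothesis as "a transportation voucher and a follow-up phone call will improve linkage". The voucher is "redeemable upon clinic linkage at any time following enrollment", including after a missed first appointment. The call goes only to intervention participants who missed that appointment. Controls receive neither.

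Section 2.3 first compares linkage by the scheduled appointment date, to assess the voucher. It then adds a second step, "To elucidate the added value of the transport voucher": it will "compare the intervention effect on linking by 30 days (overall) to the intervention effect on linkage to the scheduled appointment" and, with the Delta Method, "test the null hypothesis that the ratio of relative risks is 1 and that the difference of absolute effects is 0". The level is stated separately: "Here, we will use a two-sided test at the 5% significance level". The section does not say how a ratio above or below 1 should be read.

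Protocol 9.2.2.4 schedules the appointment within 14 days of screening, or within 3 days when blood pressure is at least 160/100 mmHg. There is therefore a period between the appointment and day 30 in which either arm can link late.

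The protocol describes a narrower intervention. Section 4.2 states: "A one-time transport voucher will increase linkage to hypertension care following community-based diagnosis". Table 9 lists only the voucher for this trial, and sections 9.2.2.4 and 14.7 tie reimbursement to linkage within 30 days.

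**The concern.** Up to the appointment, only the voucher differs between the arms. After it, three things act at once: the voucher that is still valid, the call, and ordinary late linkage in both arms. The change in the arm contrast from appointment to day 30 is a mixture of these. With two arms, and both components given together in one of them, the mixture cannot be taken apart.

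In addition, neither stated null means that nothing further happened after the appointment. A significant ratio could be taken as evidence about the voucher or the call when it reflects only the way cumulative linkage fills in. A non-significant ratio could hide a large late effect.

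**Working it through.** **The plan's own figure.** The SAP appendix gives 80% power at 100 per arm for 50% versus 69.3% linkage at 30 days. A two-sided 5% two-proportion calculation gives 79.9%, so this reproduces. Neither document gives power or any other operating characteristic for the comparison in section 2.3.

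**Model.** Let p be the probability of linking by the appointment and q the probability of linking by day 30 among those who did not. Then 30-day linkage is P = p + (1 − p)q. Subscript 1 is intervention, 0 is control.

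**No late effect of anything (q₁ = q₀ = q).**
- Risk difference at 30 days: P₁ − P₀ = (p₁ − p₀)(1 − q), smaller than p₁ − p₀ whenever p₁ > p₀ and q > 0.
- Ratio of relative risks: (P₁/P₀)/(p₁/p₀) = [q/p₁ + (1 − q)] / [q/p₀ + (1 − q)], below 1 under the same conditions.

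**When the nulls do hold.**
- If p₁ = p₀ and q is equal, the ratio is 1 and the difference 0, however many controls link late.
- The ratio null also holds if P₁/p₁ = P₀/p₀, that is, if late gains are proportional to early linkage.
- The difference null also holds if P₁ − p₁ = P₀ − p₀, that is, if absolute late gains are equal.

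**Numbers.** Control linkage of 50% at 30 days and 100 per arm come from the SAP appendix. Linkage by the appointment is not given, so p₀ and the appointment relative risk are assumptions shown over a range. Then q = (0.50 − p₀)/(1 − p₀), applied in both arms.

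One cell in full: p₀ = 0.30, relative risk 1.5, so p₁ = 0.45.
- q = 0.20/0.70 = 0.286
- P₁ = 0.45 + 0.55 × 0.286 = 0.607
- 30-day relative risk = 0.607/0.50 = 1.214; ratio = 1.214/1.5 = 0.81
- Risk difference goes from 0.150 to 0.107, a change of −0.043

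Rejection rates are from 20,000 simulated trials per cell with unadjusted estimates. The outcomes are nested, so the log-ratio variance is (1/p − 1/P)/n per arm. For the difference test it is L(1 − L)/n per arm, with L = P − p.

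| p₀ | Appointment RR | Ratio of RRs | Change in risk difference | Ratio test rejects | Difference test rejects |
|---|---|---|---|---|---|
| 0.20 | 1.3 | 0.83 | −0.023 | 12% | 7% |
| 0.20 | 1.8 | 0.67 | −0.060 | 51% | 16% |
| 0.30 | 1.3 | 0.87 | −0.026 | 15% | 8% |
| 0.30 | 1.8 | 0.75 | −0.069 | 64% | 26% |
| 0.40 | 1.3 | 0.92 | −0.020 | 13% | 8% |
| 0.40 | 1.8 | 0.85 | −0.053 | 58% | 32% |
| 0.48 | 1.3 | 0.98 | −0.006 | 4% | 4% |
| 0.48 | 1.8 | 0.97 | −0.015 | 9% | 9% |

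With an appointment relative risk of 1, both tests reject in about 4-5% of trials for p₀ from 0.20 to 0.40.

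**The converse.** Take p of 0.60 versus 0.40 and control q = 0.30, so P₀ = 0.40 + 0.60 × 0.30 = 0.58. A ratio of exactly 1 needs P₁ = 0.58 × 1.5 = 0.87, so q₁ = (0.87 − 0.60)/0.40 = 0.675. That is a late effect of 67.5% against 30%, and the ratio test rejects in only 5% of such trials. The difference null is met at another value: P₁ = 0.58 + 0.20 = 0.78, so q₁ = 0.18/0.40 = 0.45.

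**The case against.** The strongest reply is that the damage is conditional and limited. A reader might infer that the nulls are false by construction, or that the ratio leaves 1 whenever controls catch up. The documents do not support that. Without an effect by the appointment, and with equal late linkage, both nulls are true and both tests hold close to 5%. Proportional late gains keep the ratio at 1, and equal absolute late gains keep the difference at 0. The ratio test is also the worse of the two, and if 48% of controls link by the appointment its rejection rate is only about 4-9%. Nothing in the documents excludes early linkage of that order. All of this stands, and it limits the size of the point.

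It is also fair that much of the remedy is already planned. Section 2.3 opens by assigning the voucher effect to the appointment-date comparison, as does protocol 15.2. SAP 2.2 attributes the 30-day result to the intervention as a whole and plans a graph of cumulative linkage by arm. The SAP nowhere says that rejection would show a voucher effect. A reader should therefore not infer that the primary analysis is compromised or that the SAP commits itself to a false claim.

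None of this rescues the comparison for its stated purpose. Even in cells with little distortion, the call and late voucher use occur in the same arm over the same period, so no result can be assigned to one of them.

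**Conclusion.** The point holds for the supplementary comparison in SAP 2.3. As labelled, it cannot show what the voucher adds, and it cannot separate voucher from call.

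Over the assumed range (20-40% of controls linked by the appointment, 50% at 30 days, appointment relative risk 1.3-1.8, equal late linkage among non-linkers), the ratio is 0.67-0.92 with no late effect at all. Rejection is about 12-64% for the ratio test and 7-32% for the difference test. These rates rest on assumed appointment-date linkage and unadjusted estimates; covariate adjustment would alter the precision but not the marginal quantities compared. That the components cannot be separated does not depend on those assumptions.

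The primary 30-day test is unaffected. So is the appointment-date endpoint, which precedes any call and does isolate the voucher up to that date. The difference between the protocol's voucher-only description and the SAP's two-part intervention is a separate consistency matter and is no evidence about the ratio test.

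**What to change.** In SAP 2.3:
- Drop both tests as evidence on the voucher, or keep them under a label saying that they describe how the arm contrast changes between the appointment and day 30.
- State that the voucher effect is the appointment-date contrast already planned, and that the 30-day contrast is for voucher plus call.
- Report linkage after the appointment by arm, descriptively, beside the planned cumulative-linkage graph. If it is shown only among those who missed the appointment, note that this group is selected after randomisation.

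Separately, reconcile protocol 4.2, Table 9, 9.2.2.4 and 14.7 with the SAP's opening description, on whether a call is part of the intervention and on the period in which the voucher can be redeemed.

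The cost is wording in two documents and the removal or retitling of one supplementary comparison. No new data are needed, and the sample size and primary analysis do not change.

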2.6 Assess individual-level predictors of linkage to care, control, and retention in care

[figure not shown]
We will evaluate the following predictors of linkage to care within 30 days: sex, age, country, baseline HTN severity (grade), and baseline HIV status (assessed via testing and self-report). In the primary analysis, TMLE will be used to obtain variable importance measures, capturing the amount of information that a given predictor provides after adjusting for the other predictors. For each of the predictors, we will report the adjusted variables importance measures on the relative scale, treating each baseline predictor in turn as the “exposure” variable, and the rest as the adjustment set. In secondary analyses, we will calculate and report unadjusted (i.e., univariate) associations. We will conduct these analyses overall and stratified by randomized arm. Pooled analyses will include randomization arm as a predictor.

Analogous methods are used to evaluate the predictors of HTN control at 3, 6, and 12 months and retention in care at 3, 6 and 12 months.

Appendix: Power calculations

Sample size and power calculations were based of standard formulas for a two-sample test of proportions and done with *power.prop.test* in *R*.¹² We expect these calculations to be conservative, because of the precision gained through stratified randomization, through covariate adjustment during the analysis, and through our use of a one-sided hypothesis test.

We estimated 100 participants/arm would provide 80% power to detect at least a 19.3% absolute increase in linkage within 30 days from 50% under the control. As shown in the following Figure, even with 25% fewer participants enrolled (from 100 to 75 participants/arm) and lower or higher linkage under the standard-of-care, these calculations suggest we would be well-powered to detect at least a 22.7% absolute increase in linkage.

References

4. van der Laan M, Rose S. *Targeted Learning: Causal Inference for Observational and Experimental Data*. Springer; 2011.
5. Moore KL, van der Laan MJ. Covariate Adjustment in Randomized Trials with Binary Outcomes: Targeted Maximum Likelihood Estimation. *Stat Med*. 2009;28(1):39-64. doi:10.1002/sim.3445

6. Rosenblum M, van der Laan MJ. Simple, Efficient Estimators of Treatment Effects in Randomized Trials Using Generalized Linear Models to Leverage Baseline Variables. *Int J Biostat.* 2010;6(1):Article 13. doi:10.2202/1557-4679.1138
7. van der Laan MJ, Rose S. *Targeted Learning in Data Science*. Springer; 2018.
9. Balzer LB, van der Laan M, Ayieko J, et al. Two-Stage TMLE to Reduce Bias and Improve Efficiency in Cluster Randomized Trials. *Biostatistics.* 2021;kxab043. <https://doi.org/10.1093/biostatistics/kxab043>
11. Balzer L, van der Laan MJ, Petersen M, SEARCH Collaboration. Adaptive Pre-specification in Randomized Trials With and Without Pair-Matching. *Stat Med.* 2016;35(10):4528-4545. doi:10.1002/sim.7023
12. R Core Team. *R: A Language and Environment for Statistical Computing*. R Foundation for Statistical Computing; 2020. <http://www.R-project.org>

Sustainable East Africa Research in Community Health (SEARCH) Collaboration

Statistical Analysis Plan for Dynamic Choice Care Intervention for Mobile Persons with HIV in Phase A of SEARCH-Sapphire

[name], PhD¹
and the SEARCH Study Team²

May 19, 2022

v1.0

¹University of California, Berkeley

²www.searchendaids.com

Table of Contents:

1. Study Overview	2
2. Population and Characteristics	3
3. Endpoint Measurement and Definition	3
4. Evaluation of the SEARCH Intervention Effect	4
5. Intervention Implementation	5
Appendix: Power calculations	5
References	6

1. Study Overview

In Phase A of SEARCH-Sapphire (NCT04810650), we are conducting an individually randomized controlled trial to evaluate the effect of dynamic choice, patient-centered care intervention for mobile persons with HIV (PWH) in rural Kenya and Uganda. Details of the trial design and procedures can be found in the corresponding Study Protocol. Analyses plans for qualitative outcomes and cost-effectiveness outcomes are available elsewhere. Power calculations are given in the Appendix.

In brief, from April through July 2021, we enrolled 201 mobile PWH who were at risk of viral non-suppression. These participants were randomized to the intervention or the standard-of-care using a stratified random block design with stratification factors of country and sex and with random block sizes of 2 and 4. The randomization list was generated by an independent researcher.

The intervention includes choice of the following components to address barriers to HIV care among mobile PWH:

- Travel pack, including emergency antiretroviral therapy (ART) supply, discrete ART packaging, and a travel checklist
- Hotline access to a mobility coordinator
- Offsite and longer ART refills
- Facilitated access to ART and HIV care outside of the community

The intervention is delivered by a mobility coordinator, stationed at each clinic, and follow-up is over 48 weeks.

The primary objective is to evaluate if the intervention improved viral suppression (<400 copies/mL) among mobile PWH at week-48. Secondary endpoints, compared

between randomized arms, include retention in HIV care and ART possession. Additionally, within the intervention arm, we will report coverage and uptake of the intervention components at both scheduled and unscheduled visits.

2. Population and Characteristics

The population of interest is PWH who are aged 15+ years, enrolled or new to HIV care, at risk of viral non-suppression (HIV RNA>400 copies/mL in the past year or 2+ missed HIV care visits in the past year), and mobile (2+ weeks out of the community in the past year).

To characterize measurement of this population, we will provide a participant flow diagram (i.e., a CONSORT diagram). Overall and stratified by trial arm and further by sex, we will summarize the baseline characteristics, including sex, age, country, marital status, occupation, education level, alcohol use (any use in past 3 months), mobility metrics (nights away in past 3 months and in past 12 months), impact of mobility on HIV care (missed visits and missed ART doses), baseline ART status and regimen, baseline viral suppression status, and trial enrollment criteria. We will categorize age as “younger” if aged 15-30 years and define persons to be “highly mobile” if they report spending >14 nights away from the community in the past 3 months.

3. Endpoint Measurement and Definition

The **primary endpoint** is HIV viral suppression (HIV RNA<400 copies/mL) at 48-weeks. The primary analytic population consists of all living study participants who have not transferred HIV care to another health facility (as documented in clinical records). In other words, the primary analysis will exclude persons who died, withdrew, or transferred care, but will, otherwise, include persons regardless of their level of mobility or history of movement in/out of the community. In the primary analysis, missing endpoint viral loads will be treated as failures (i.e., unsuppressed). In pre-specified sensitivity analyses, described below, we will assess the robustness of these analytic choices.

Based on review of Ministry of Health medical and pharmacy records, we will also examine the following **secondary endpoints**:

- Retention in care: the proportion of follow-up time where the participant is engaged in clinical care
- ART possession: the proportion of follow-up time where the participant has a full regimen of ART

We will calculate total follow-up time for each participant as the number of days from their trial enrollment to their week-48 viral load measure. (For persons without a week-48 viral load measure, we will use the close the endpoint ascertainment window.) Out-of-care time will start 14 days after a missed visit and end at re-engagement in care.

4. Evaluation of the SEARCH Intervention Effect

We will assess the intervention effect with targeted minimum loss-based estimation (TMLE), which improves precision and power by adaptively adjusting for baseline outcome predictors.^{1–5} Here, we will use **TMLE with Adaptive Pre-specification** to flexibly control for baseline covariates, while maintaining Type-I error control and accounting for the randomization scheme.^{6–8} Using 10-fold cross-validation, we will choose the optimal approach for estimating the outcome regression (i.e., the expected outcome given the randomization arm and adjustment covariates) and the known propensity score (i.e., the conditional probability of being randomized to the intervention given the adjustment covariates). Specifically, we will select the combination of estimators (adjustment variables + approach) that minimizes the cross-validated variance estimate.

Our pre-specified, candidate adjustment variables consist of sex, age, country, being new to care at enrollment, baseline mobility (number of nights away from the community in the past 12 months), baseline viral suppression status, and nothing (i.e., unadjusted). Our pre-specified, candidate learners consist of generalized linear models (GLMs) adjusting for a single variable beyond the intervention indicator, stepwise regression, multivariate adaptive regression splines (MARS), MARS after screening based on outcome correlations, and the arm-specific mean outcome.

Primary effect estimates will be for the study sample and on the **ratio scale**:

$1/n \sum_{i=1}^n Y_i(1) \div 1/n \sum_{i=1}^n Y_i(0)$, where $Y_i(1)$ denotes the counterfactual outcome for participant i under the intervention and $Y_i(0)$ denotes the counterfactual outcome for participant i under the control.^{9–11} Secondary comparisons will be on the difference scale.

We will test the **null hypothesis** that the intervention did not improve viral suppression at week-48 using a one-sided test at the 5% significance level. We will also report point estimates and 95% confidence intervals for each effect measure and the arm-specific outcomes at baseline and week-48. Standard error estimation will be based on the estimated influence curve, and statistical inference will follow from the Central Limit Theorem (i.e., using the standard normal distribution).¹

Secondary analyses: To assess the robustness of these findings, we will repeat these analyses using the unadjusted effect estimator. We will also repeat these analyses excluding persons with missing endpoints and using TMLE to adjust for missing endpoints.

Subgroup analyses: We will repeat these analyses within strata defined by country, sex, age group, mobility level, alcohol use, baseline viral suppression status, and trial enrollment criteria. In subgroups analyses, we will limit the candidate estimation approaches to main terms adjustment for a single covariate or the simple mean and use leave-one-out cross-validation for subgroups with <40 participants. To further understand effect heterogeneity, we may conduct variable importance measures (unadjusted and adjusted) to understand baseline predictors of endline viremia, overall and by arm.

Secondary endpoints compared by arm: We will implement analogous analyses to evaluate the intervention effect on retention in care and ART possession.

5. Intervention Implementation

Within the intervention arm, we will describe coverage and uptake of the intervention at baseline (week-0), week-12, week-24, and week-36 study visits:

- Visit coverage: number and proportion who attended study visits
- Choice of intervention components: number and proportion* who selected the travel pack, longer ART refills, off-site refills, and/or facilitated out-transfer
- Stocking and re-stocking of travel pack components: number and proportion* who selected the hotline, emergency ART, the travel checklist, and/or discrete ART packaging
- Choice of visit type: number and proportion who had visits in-person at the clinic, in-person in the community, or virtually on the mobile hotline

[figure not shown]
*Since participants could select more than one component, the proportion for a given visit-week may exceed 100%. Additionally, for unscheduled visits, we will report analogous metrics in terms of ever choice or use. We may also report summaries of the travel screen conducted by the mobility coordinator at each visit.

